6.5.4.1 Routine laboratory

Routine laboratory measurements include clinical chemistry and hematology. They will be measured at all time points specified in Table 6-1.

Hematology: Hemoglobin, hematocrit, red blood cell count, white blood cell count with differential (neutrophils including bands, lymphocytes, monocytes, eosinophils, basophils) and platelet count.

Clinical chemistry/ proteins: Urea, creatinine, total bilirubin, AST (SGOT), ALT (SGPT), GGT, alkaline phosphatase, creatinine, sodium, potassium, bicarbonate, calcium, phosphorous, total protein, albumin, uric acid, amylase, lipase, hsCRP, HbA1c (only at visits 1, 2, 7, 9, 11, 12, E1, E2, E3 included), fructosamine (only at visits 1, 2, 6, 7, 8, 9, 10, 11, 12, E1, E2, E3 included).

6.5.4.2 Fasting laboratory

Fasting laboratory measurements will be made at all time points specified in Table 6-1. **Fasting for 8 hours duration with water ad libitum is required prior to blood draws.** Subjects should avoid smoking within in the hours preceding the blood draws.

Fasting laboratory: Total cholesterol, triglycerides, HDL, LDL, fasting plasma glucose.

6.5.4.3 Urinalysis

Dipsticks will be provided by the central laboratory to the study sites for local urinalysis assessments. Standard dipstick measurements for specific gravity, nitrite, protein, glucose, pH, blood, urine blood dipstick (non-hemolyzed), urine blood dipstick (hemolyzed), urobilinogen, bilirubin, ketones and WBC will be done at scheduled visits as indicated in Table 6-1. If needed conditional microscopy assessments will be optional and will be performed locally.

6.5.5 Electrocardiogram (ECG)

Not applicable in this study.

6.5.6 Pregnancy and assessments of fertility

In all women who are not sterilized or are of childbearing potential a serum pregnancy test (β -hCG) must be performed as indicated in Table 6-1.

Any woman with a confirmed positive pregnancy test during Screening is not eligible for randomization. A positive serum pregnancy test during the treatment phases of the study requires immediate interruption of study treatment.

6.5.7 Appropriateness of safety measurements

The safety assessments selected are standard measures for a biologic immunomodulating agent in Psoriasis.

The safety assessments selected are standard for this indication/patient population.

6.6 Other assessments

6.6.1 Clinical Outcome Assessments (COAs)

6.6.1.1 Clinician Reported Outcomes (ClinRO)

Not applicable.

6.6.1.2 Patient Reported Outcomes (PRO)

Patient reported outcomes will be assessed by the following validated instruments, each of which will be performed as indicated in Table 6-1:

- Dermatology Life Quality Index (DLQI[®])
- Self-assessed pain, itching, scaling
- WHO-5

All these quality of life assessments should be completed by the subject before they see the study physician (investigator or designee) who will perform the investigator assessments.

All these quality of life assessments will be completed **in German language**. The subject should be given sufficient space and time to complete the questionnaires. The study coordinator should check the questionnaires for completeness and encourage the subject to complete any missing responses. Prior to clinical examination, the investigator should review the completed

questionnaires for responses that may indicate potential AEs or SAEs. If AEs or SAEs are confirmed, the investigator must record the events as per instructions given in Section 7 of the protocol.

Investigators should not encourage subjects to change the responses reported in the completed questionnaires.

Dermatology Life Quality Index (DLQI®)

The DLQI® is a 10-item general dermatology disability index designed to assess Health-related quality of life (HRQoL) in adult subjects with skin diseases such as eczema, psoriasis, acne, and viral warts (Finlay and Khan, 1994; Basra et al., 2008).

The measure is self-administered and includes domains of daily activities, leisure, personal relationships, symptoms and feelings, treatment, and work/school. The measure is widely used: it has been tested across 33 different skin conditions and is available in 85 languages. The DLQI is the most frequently used instrument in studies of randomized controlled trials in dermatology. The recall period is the previous week, and the instrument takes 1 to 2 minutes to complete.

Each item has four response categories ranging from 0 (not at all) to 3 (very much). “Not relevant” is also a valid response and is scored as 0. The DLQI® total score is a sum of the 10 questions. Scores range from 0 to 30, with higher scores indicating greater HRQoL impairment. Each subscale of the DLQI® may also be analyzed separately.

Subject’s self-assessed pain, itching and scaling

A self-administered, 11-point numeric rating scale (NRS, 0-10) will be used to evaluate the subject’s assessment of their current pain, itching and scaling. Respondents will answer the following questions for the assessment of

Pain: Overall, how severe was your psoriasis-related pain over the past 24 hours

Itching: Overall, how severe was your psoriasis-related itch over the past 24 hours

Scaling: Overall, how severe was your psoriasis-related scaling over the past 24 hours

Subjects have to rate their pain, itching, and scaling from 0 to 10 (11-point scale), with the understanding that the 0 represents the absence or null end of the pain, itching, or scale intensity (i.e., no pain, itching or scaling) and the 10 represents the other extreme of pain, itching, or scaling intensity (i.e., pain, itching or scaling as bad as it could be). The number that the patient selects represents his or her intensity score.

WHO-5

The 5-item World Health Organization Well-Being Index (WHO-5) is a validated, short questionnaire consisting of 5 simple questions, assessing subjective psychological well-being of the respondents. It is among the most widely used questionnaires for the assessment of psychological well-being and has been successfully applied across a wide range of study fields.

The measure is self-administered and takes approximately one minute to complete. The recall period is the previous two weeks. Each item has 6 response categories, ranging from 5 (“the whole time”) to 0 (“at no time point”). The WHO-5 total score is the sum of the 5 questions. Each subscale of the WHO-5 may also be analyzed separately.

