| 
 To explore treatment efficacy of Secukinumab (300 mg, 4-weekly s.c.) combined with lifestyle intervention in comparison to Secukinumab alone To evaluate the effect of Secukinumab (300 mg, 4-weekly s.c.) combined with lifestyle intervention in comparison to Secukinumab alone on systemic inflammation To evaluate the effect of Secukinumab (300 mg, 4-weekly s.c.) combined with lifestyle intervention in comparison to Secukinumab alone on glucose metabolism To evaluate the effect of Secukinumab (300 mg, 4-weekly s.c.) combined with lifestyle intervention in comparison to Secukinumab alone on lipid metabolism To evaluate the effect of Secukinumab (300 mg, 4-weekly s.c.) combined with lifestyle intervention in comparison to Secukinumab alone on body weight and waist circumference To evaluate the effect of Secukinumab (300 mg, 4-weekly s.c.) combined with lifestyle intervention in comparison to Secukinumab alone on systolic and diastolic blood pressure To evaluate the effect of Secukinumab (300 mg, 4-weekly s.c.) combined with | 
 PASI75, 90 and 100 as well as absolute PASI scores in both treatment arms at week 1, 2, 3, 4, 8, 12, 16, 20, 24 and 28 hsCRP in both treatment arms throughout the duration of the core study HbA1c, fructosamine and fasting plasma glucose in both treatment arms throughout the duration of the core study Total cholesterol, LDL, HDL and triglycerides in both treatment arms throughout the duration of the core study Waist circumference, body weight and BMI in both treatment arms throughout the duration of the core study Systolic and diastolic blood pressure in both treatment arms throughout the duration of the core study Absolute DLQI, relative change of DLQI, proportion of patients with |

| Objective(s) | Endpoint(s) |
|--|---|
| lifestyle intervention in comparison to Secukinumab alone on health-related quality of life, itch, pain and scaling as well as mental well-being | DLQI 0/1, absolute WHO-5, relative change in WHO-5, absolute self-assessed itch, pain, scaling, relative change in self-assessed itch, pain, scaling in both treatment arms throughout the duration of the core study |

| Objective(s) | Endpoint(s) |
|---|---|

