3.2 Rationale for study design

This study design was chosen in order to be able to demonstrate that the combination of Secukinumab (300 mg, 4-weekly s.c.) with lifestyle intervention results in higher psoriasis treatment efficacy compared to Secukinumab alone in psoriasis patients with concomitant metabolic syndrome. Therefore a randomized study set up with two treatment arms was chosen, arm B, where patients receive Secukinumab treatment combined with lifestyle intervention and arm A as active comparator control group, where patients receive Secukinumab alone.

The design enables assessment of the additional effects of concomitant lifestyle intervention on psoriasis treatment efficacy of Secukinumab as well as on metabolic status of the patients.

The open-label design is a consequence of the lifestyle intervention, which would be very difficult to blind. This might theoretically lead to a certain bias concerning psoriasis severity assessments (PASI), as investigators could expect patients receiving additional lifestyle intervention to show stronger improvements. On the other hand lifestyle intervention is no drug therapy and is not established as therapeutic intervention in psoriasis therapy, which limits the bias. Furthermore the study includes an extension period, which offers lifestyle intervention to

all patients and which includes a final PASI assessment at the end of the extension period, thereby further limiting the bias. Other, secondary objectives, like improvement of glucose and lipid metabolism, reduction of blood pressure, weight loss or changes in biomarker levels are based on laboratory parameters (HbA1c, lipid panel, biomarkers) or technical measurements (blood pressure, body weight), where the influence of a potential bias is highly limited.

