5.4 Treatment blinding

Not applicable, as this study has an open label design.

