6.4.1 PASI/ BSA

Assessment of total body surface area (BSA) and Psoriasis Area and Severity Index (PASI)

The investigator or trained qualified designee will complete the PASI assessment as indicated in Table 6-1. Whenever possible, the same evaluator should perform this assessment at all visits.

The total BSA affected by plaque-type psoriasis will be estimated from the percentages of areas affected, including head, trunk, upper limbs and lower limbs (see below for full details of the PASI assessment). The following calculations will be done: Each reported percentage will be multiplied by its respective body region corresponding factor (head = 0.1, trunk = 0.3, upper limbs = 0.2, lower limbs = 0.4). The resulting four percentages will be added up to estimate the total BSA affected by plaque-type psoriasis.

The PASI scoring system is further described in Table 6-3.

A PASI score (Fredriksson and Pettersson, 1978; Weisman et al., 2003; Gottlieb et al., 2005) will be derived as indicated in Table 6-3. The head, trunk, upper limbs and lower limbs are assessed separately for erythema, thickening (plaque elevation, induration), and scaling (desquamation). The average degree of severity of each sign in each of the four body regions is assigned a score of 0-4. The area covered by lesions on each body region is estimated as a percentage of the total area of that particular body region. Further practical details to help with the assessment are provided below:

1. The neck is assessed as part of the head
2. The axillae and groin are assessed as part of the trunk
3. The buttocks are assessed as part of the lower limbs

4. When scoring the severity of erythema, scales should not be removed.

Because the head and neck, upper limbs, trunk and lower limbs correspond to approximately 10%, 20%, 30% and 40% of the body surface area, respectively, the PASI score is calculated using the formula:

$$\text{PASI} = 0.1(E_H + I_H + D_H)A_H + 0.2(E_U + I_U + D_U)A_U + 0.3(E_T + I_T + D_T)A_T + 0.4(E_L + I_L + D_L)A_L$$

The keys for the letters are provided in Table 6-2.

PASI scores can range from a lower value of 0, corresponding to no signs of psoriasis, up to a theoretic maximum of 72.0.

The baseline value for analysis of the PASI is collected at the Randomization Visit.

If results of BSA and PASI assessment fulfill criteria for an (serious) adverse event, the investigator has to document it accordingly.

Table 6-2 The PASI scoring system

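### The protocol has the investigator review patient questionnaires before examination and does not separate that review from PASI scoring, leaving an avoidable cue to an unblinded rater of the primary endpoint

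*Protocol*

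**What the plan says.** Protocol 6.6.1.2 requires the questionnaires to be "completed by the subject before they see the study physician (investigator or designee) who will perform the investigator assessments". It then gives the step in question: "Prior to clinical examination, the investigator should review the completed" "questionnaires for responses that may indicate potential AEs or SAEs". The verb is should, and the stated purpose is safety screening.

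On who scores the primary endpoint, Protocol 6.4.1 says: "The investigator or trained qualified designee will complete the PASI assessment as indicated in Table 6-1". It asks for the same evaluator at all visits where possible. It does not require the evaluator to be someone other than the person who read the questionnaires, or to be kept from them.

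On blinding, Protocol 5.4 says: "Not applicable, as this study has an open label design". Section 8.5 provides for no adjudication. Section 3.2 admits that "investigators could expect patients receiving additional lifestyle intervention to show stronger improvements" and that PASI could be biased as a result, but it does not mention the questionnaire review.

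The questionnaires are also outcomes. The last secondary objective in Protocol Table 2-1 concerns the effect of "lifestyle intervention in comparison to Secukinumab alone on health-related quality of life, itch, pain and scaling as well as mental well-being".

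**The concern.** The sole primary endpoint, PASI90 at Week 28, is a clinician's graded score turned into yes or no at a threshold. One of its three signs is scaling, graded 0 to 4 in each of four body regions. The patient has just rated psoriasis-related scaling from 0 to 10 on a form that the investigator is directed to review before examining.

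The rater already knows the arm. The forms may add a second cue, with content that overlaps directly with a component of the score. If the answers are on average better in one arm, as the secondary objective sets out to test, that cue differs by arm and could move borderline PASI grades in the same direction. A shift of that kind cannot be separated from a skin effect afterwards. The only sensitivity analysis shown for the primary endpoint (Protocol 9.4.4, SAP 2.5.4) is a centre-stratified CMH test on the same ratings.

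**Working it through.** The point turns on sequence, so the main check sets the provisions side by side.

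1. **Is an order prescribed?** Protocol 5.5.4 says that Section 6 gives the flow of work, including the clinical outcome assessments. Section 6.6.1.2 puts patient completion first, then investigator review, then clinical examination. Section 6.4 says that everything comes before dosing. Nothing in 6.4 or 6.4.1 places PASI before the review.

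2. **Does clinical examination take in PASI?** The term is not defined. Table 6-1 schedules the physical examination only at Visits 1, 2, 9, 12 and E3. DLQI, WHO-5 and the symptom scales are also collected at Weeks 4, 8, 12, 20 and 24, where PASI/BSA is the only scheduled clinician examination of the skin. Including PASI is the natural reading at those visits, though it is not stated. At Week 28 the questionnaires, PASI and the physical examination all fall due.

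3. **Is the rater shielded?** No. Rater and reviewer may be the same person, and no masking is required.

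4. **How coarse is PASI near the cut-off?** PASI90 needs a score at or below 0.1 × baseline. One grade of one sign on the lower limbs changes PASI by 0.4 × 1 × area score, which is 0.4 at area score 1 and 0.8 at area score 2. Entry requires PASI above 10. The documents give no typical baseline, so the values below are assumptions:
 - baseline 10 (lower limit): cut-off 1.0; one grade is 0.4/1.0 = 40% or 0.8/1.0 = 80% of it
 - baseline 20: cut-off 2.0; one grade is 20% or 40%
 - baseline 30: cut-off 3.0; one grade is 13% or 27%

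 This shows that a single grade can decide response in a borderline patient. It is not evidence that any grade is moved.

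5. **The plan's own figure.** With 81% vs 90%, two-sided alpha 0.05 and power 90%:

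 n = [1.960 × √(2 × 0.855 × 0.145) + 1.282 × √(0.81 × 0.19 + 0.90 × 0.10)]² / 0.09² = 320 per arm.

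 With the continuity correction, (n/4) × [1 + √(1 + 4/(n × 0.09))]², using the unrounded n of 319.6, gives 342, as stated. Continuity-corrected power at 342 is 90.1% for 9 points and 74.7% for 7.5 points, matching the stated 90% and 75%. Dividing by 0.90 gives 380, an implied dropout of 10%. The sample size is not in question.

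6. **How sensitive is the test to rater bias from any cause?** Assume no true effect (81% in both arms) and a rating shift of b in arm B. The chance of a false superiority claim is Φ{[b − 1.96 × √(2p̄(1−p̄)/n)] / √[(p₁(1−p₁) + p₂(1−p₂))/n]}, with p₁ = 0.81, p₂ = 0.81 + b and p̄ their mean:

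| Assumed total shift b | 342 per arm | 380 per arm |
|---|---|---|
| 0 | 2.5% | 2.5% |
| 1 point | 5.2% | 5.4% |
| 2 points | 10.0% | 10.7% |
| 3 points | 17.7% | 19.2% |

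A 2-point shift means that 0.02/0.19 = 10.5% of arm B non-responders are rated as responders. These shifts are assumptions about rater bias as a whole. The documents give no way to say what part, if any, would come from reading the questionnaires.

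**The case against.** The strongest reply is that this adds little to a limitation that is already disclosed. The rater knows the arm, and Section 3.2 says so openly. Section 7.1 has adverse events sought by questioning at every visit, so patients can tell the investigator how they feel whatever the order of the forms. A trained delegate may score PASI, so a site can follow 6.6.1.2 to the letter with a rater who has seen nothing. All of this stands, and it limits the value of the change.

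Several stronger readings are tempting, and the documents do not support them:

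- **That the protocol compels the rater to read the answers.** The text says should, limits the purpose to adverse event signals, and does not name the PASI rater.
- **That the rater is in fact influenced.** This is plausible but not shown anywhere.
- **That the effect acts in arm B alone.** The review applies to both arms, and arm A patients, with 81% expected PASI90, should also report mild symptoms. The Visit 2 questionnaires fall under the same sequence, so baseline PASI does too. Only a between-arm difference in answers could bias the comparison.
- **That all the instruments respond to lifestyle change without any change in the skin.** DLQI is dermatology-specific, and the itch, pain and scaling items ask about psoriasis-related symptoms. Only WHO-5 is generic.
- **That agreement between PASI and the questionnaires would lose its value as support.** The forms are completed before the physician is seen, so any dependence runs one way, from questionnaire to rating.

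What the reply does not answer is that the protocol sets an order, the order places the patient's self-ratings before examination, and nothing protects the scoring. The mitigations in 3.2 do not reach this route. In particular, the Week 56 PASI follows free choice of psoriasis therapy and lifestyle intervention offered to both arms, so it cannot check Week 28.

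**Conclusion.** The point holds as a gap in procedure: the adverse event review of the questionnaires is not separated from PASI scoring, so an unblinded rater may also be influenced by the patient's reports. Bias in the treatment comparison needs three things together: the rater has seen the answers, the answers differ by arm, and they affect the grading. The documents permit the first, set out to test the second, and are silent on the third.

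The size cannot be estimated. A reader might assume a percentage of patients tipped over the threshold and express it as a share of the planned 9 points. Such a figure would describe rater expectation in total and cannot be charged to this sequence. The table of false superiority rates shows only why avoidable cues are worth removing from this endpoint. The gain from the change is modest, and the conceded open-label bias remains.

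**What to change.** State the same order in Protocol 6.4.1 and 6.6.1.2 for every visit with questionnaires:

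1. The patient completes the questionnaires before seeing the physician, as now.
2. The rater scores and records PASI/BSA without having seen the answers.
3. The investigator reviews the questionnaires for possible adverse events and completes the examination.
4. The injection follows.

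This keeps both existing rules, questionnaires first and all assessments before dosing, and keeps the adverse event check at the same visit. The cost is amended wording, approved as Section 11.1 requires, and a site instruction. There is no added staff, visit or procedure. The downsides are that the questionnaire review happens minutes later and that the rater still knows the arm. The change has to be made in conduct, because the planned CMH sensitivity analysis reuses the same ratings and cannot undo an influence on them.

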6.6.1.3 Performance Outcomes (PerfO)

Not applicable.

6.6.1.4 Observer Reported Outcomes (ObsRO)

Not applicable

6.6.1.5 Proxy Reported Outcomes

Not applicable.

6.6.2 Resource utilization

Not applicable.

6.6.3 Pharmacokinetics

Not applicable.

6.6.4 DNA sampling

Not applicable.

Pharmacogenetics

Not applicable.

6.6.5 Biomarker substudy

A biomarker sub-study will be performed during the core study to explore the effect of Secukinumab (300 mg, 4-weekly s.c.) combined with lifestyle intervention in comparison to Secukinumab alone on biomarkers including but not limited to those linked to lipid, glucose, muscle and bone metabolism, liver fibrosis/steatosis, heart failure, as well as to inflammatory processes in a subgroup of 100 patients (50 treated with secukinumab and lifestyle intervention and 50 treated with Secukinumab alone). At baseline (week 0), week 16 and week 28 the following markers will be assessed using fasting blood samples: Free fatty acid serum profile, sThy-1, adiponectin, leptin, insulin, HOMA-IR, proinsulin, IL-6, TNF-alpha, M30 assay, IL-1 beta, IL-1Ra, IL-18, IL-18bp, P1NP, CTX, RANKL, OPG, sclerostin, NT-proBNP, CD154, and a 30-panel multiplex inflammatory cytokine and chemokines panel.

The markers will be assessed centrally.

7 Safety monitoring

7.1 Adverse events

An adverse event (AE) is any untoward medical occurrence (e.g., any unfavorable and unintended sign [including abnormal laboratory findings], symptom or disease) in a subject or clinical investigation subject *after providing written informed consent* for participation in the study until the end of study visit. Therefore, an AE may or may not be temporally or causally associated with the use of a medicinal (investigational) product. Medical conditions/ diseases

present before first intake of study drug are only considered adverse events if they worsen after study start.

In addition, all reports of intentional misuse and abuse of the product are also considered an adverse event irrespective if a clinical event has occurred.

The occurrence of adverse events must be sought by non-directive questioning of the patient at each visit during the study. Adverse events also may be detected when they are volunteered by the patient during or between visits or through physical examination findings, laboratory test findings, or other assessments.

Abnormal laboratory values or test results constitute adverse events only if they fulfill at least one of the following criteria:

- they induce clinical signs or symptoms,
- they are considered clinically significant,
- they require therapy.

Clinically significant abnormal laboratory values or test results must be identified through a review of values outside of normal ranges/clinically notable ranges, significant changes from baseline or the previous visit, or values which are considered to be non-typical in patient with underlying disease. Investigators have the responsibility for managing the safety of individual patient and identifying adverse events. Alert ranges for laboratory and other test abnormalities are included in Appendix 1. Clinically significant abnormal laboratory values will also be assessed for the following parameters of the biomarker sub-study (only for patients participating in the biomarker sub-study): Adiponectin, leptin, insulin, HOMA-IR, proinsulin, IL-6, TNF-alpha, M30 assay, NT-proBNP.

Adverse events must be recorded in the Adverse Events CRF under the signs, symptoms or diagnosis associated with them, accompanied by the following information:

- the severity grade
 - mild: usually transient in nature and generally not interfering with normal activities
 - moderate: sufficiently discomforting to interfere with normal activities
 - severe: prevents normal activities
- its relationship to the study treatment and/or to the lifestyle intervention
 - “No Relationship to study treatment and lifestyle intervention” or
 - “Relationship to study treatment” or
 - “Relationship to lifestyle intervention” or
 - “Relationship to both study treatment and lifestyle intervention or indistinguishable”
- its duration (start and end dates) or if the event is ongoing an outcome of not recovered/not resolved must be reported.
- whether it constitutes a serious adverse event (SAE - See Section 7.2 for definition of SAE) and which seriousness criteria have been met.
- action taken regarding study drug or lifestyle intervention
- its outcome (not recovered/not resolved; recovered/resolved; recovering/resolving, recovered/resolved with sequelae; fatal; or unknown)

All adverse events must be treated appropriately. The action taken to treat the adverse event should be recorded on the Adverse Event eCRF. Treatment may include one or more of the following:

- no action taken (e.g. further observation only)
- study treatment dosage increased/reduced
- lifestyle intervention intensity increased/reduced
- study treatment and/or lifestyle intervention interrupted/withdrawn
- concomitant medication given
- non-drug therapy given
- patient hospitalized/patient's hospitalization prolonged (see Section 7.2 for definition of SAE)

Once an adverse event is detected, it must be followed until its resolution or until it is judged to be permanent, and assessment must be made at each visit (or more frequently, if necessary) of any changes in severity, the suspected relationship to the study drug, the interventions required to treat it, and the outcome.

Information about common side effects already known about the investigational drug can be found in the Investigator Brochure (IB). This information will be included in the patient informed consent and should be discussed with the patient prior to and during the study as needed. Any new information regarding the safety profile of the medicinal product that is identified between IB updates will be communicated as appropriate, for example, via an Investigator Notification or an Aggregate Safety Finding. New information might require an update to the informed consent and has then to be discussed with the patient.

The investigator must also instruct each patient to report any new adverse event (beyond the protocol observation period) that the patient, or the patient's personal physician, believes might reasonably be related to study treatment. This information must be recorded in the investigator's source documents; however, if the AE meets the criteria of an SAE, it must be reported to Novartis.

